9.4.3 Safety

Safety analyses will be performed using the FAS. Safety data will be presented using descriptive statistics unless otherwise specified. In general, the baseline value for statistical analysis is the last nonmissing value prior to administration of the first dose of study intervention. Details will be described in the SAP.

9.4.3.1 Adverse Events

Adverse events will be coded using the most recent version of the MedDRA that will have been released for execution at AstraZeneca or designee.

Adverse events will be presented for each treatment group by system organ class and/or preferred term covering number and percentage of participants reporting at least one event.

Only AEs occurring with an onset date, or worsening, on or after first dose of study intervention, throughout the treatment period and including the follow-up period will be presented in summary tables. SAEs occurring prior to start of study intervention will be included in data listings.

An overview of AEs will be presented for each treatment group; the number and percentage of participants with any AE, AEs with outcome of death, SAEs, AEs leading to discontinuation of study intervention, AEs leading to study intervention dose interruptions, and AESIs.

Separate AE tables will be provided taking into consideration relationship as assessed by the investigator and maximum intensity, seriousness, death, and AEs leading to discontinuation of study intervention, as well as action taken with respect to the study intervention, and other significant AEs.

Key participant information will be presented for participants with AEs with outcome of death, SAEs, and AEs leading to discontinuation of study intervention. An AE listing for the FAS will cover details for each individual AE; an AE listing for participants who were not

exposed to study intervention is presented separately.

Full details of AE analyses will be provided in the SAP.

9.4.3.2 Vital Signs

Vital sign parameters (supine and standing blood pressure, pulse, and body temperature) will be presented for each treatment group.

For each scheduled post-baseline visit, descriptive statistics for all vital sign parameters will be presented for observed values and change from baseline.

Supportive vital sign listings cover observed values and changes from baseline as well as abnormalities.

Details of vital sign analyses including definition of abnormality criteria (eg, definition of low, normal, high) and project-specific predefined criteria for treatment-emergent changes in relevant vital sign parameters (eg, systolic and diastolic blood pressure) will be provided in the SAP.

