Vital signs (supine and standing blood pressure and pulse)	X	X (pre-dose) X (60, 120, 180 minutes)	X	X	X	X	X		Section 8.3.2
Body temperature	X	X	X	X	X	X	X		Section 8.3.2

Table 1 Schedule of Activities

	Screening period	Treatment period						Follow-up	Section in the CSP
		Randomisation	Visits						
Visit number	1	2	3	4	5	6 ^a	7		
Week	-3	0	1	2	3	6	8		
Study day	-21 to -7 ^a	1	8	15	22	43	57		
Visit window (days)			± 3	± 3	± 3	± 5	± 3		
Clinical safety laboratory tests (haematology, clinical chemistry, coagulation, electrolytes, serum osmolality, and NT-pro BNP)	X	X ⁱ	X ⁱ	X ⁱ	X ⁱ	X ⁱ	X	Section 8.3.5	
PK assessments									
Pre-dose PK plasma sample (all participants) ^j			X ⁱ	X ⁱ	X ⁱ			Section 8.5	
PK profile (Japanese)					X ^{k,1}			Section 8.5	
Post-dose sample (Non-Japanese)					X ^m			Section 8.5	

Table 1 Schedule of Activities

	Screening period	Treatment period						Follow-up	Section in the CSP
		Randomisation	Visits						
Visit number	1	2	3	4	5	6 ^a	7		
Week	-3	0	1	2	3	6	8		
Study day	-21 to -7 ^a	1	8	15	22	43	57		
Visit window (days)			± 3	± 3	± 3	± 5	± 3		
Exploratory assessments									
CCI	X ^g					X ^{fg}			Section 8.2.2.1
eGFR calculation ^a	X	X	X	X	X	X	X		Section 8.2.2.2
MELD score calculation	X	X	X	X	X	X	X		Section 8.2.2.3
Child-Pugh score	X	X	X	X	X	X	X		
Non-fasting plasma/serum biomarkers		X ⁱ			X ⁱ	X ⁱ			
HbA1c	X ⁱ	X ⁱ			X ⁱ	X ⁱ			
PROs: CLDQ, PGIS - Liver Disease, and SF-36v2 acute		X ^o				X			Section 8.2.2.4
Collect and store serum and plasma samples for exploratory assessment of biomarkers		X ⁱ				X ⁱ			Section 8.8.1

Table 1 Schedule of Activities

	Screening period	Treatment period						Follow-up	Section in the CSP
		Randomisation	Visits						
Visit number	1	2	3	4	5	6 ^a	7		
Week	-3	0	1	2	3	6	8		
Study day	-21 to -7 ^a	1	8	15	22	43	57		
Visit window (days)			± 3	± 3	± 3	± 5	± 3		
Collect and store urine samples for exploratory assessment of biomarkers		X ⁱ				X ⁱ			Section 8.8.1
Optional Genomics Initiative, exploratory genomics, and multi-omics samples		X							Section 8.7 and Appendix D

- Screening visit can take place from 21 days up to 7 days before randomisation visit (Visit 2). It must be at least 7 days between Visit 1 and Visit 2 to allow time for laboratory results to be examined.
- Brief physical examination.
- Only in those participants with history of Heart Failure and if historical data from ECHO or cardiac MRI in the prior 12 months is not available.

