8.3.2 Vital Signs

Vital signs assessments will be performed at timepoint as specified in the SoA ([Table 1](#)).

Vital signs will include supine and standing blood pressure, pulse, and body temperature measurements.

Routine blood pressure, pulse, and body temperature will be assessed at the study centre, as outlined in the SoA ([Table 1](#)), prior to blood collection for laboratory tests with the participant resting in a supine position using a completely automated device. Manual techniques will be used only if an automated device is not available.

Participants who suffer from **CCI** [REDACTED] and/or **CCI** [REDACTED] of **CCI** [REDACTED] during the course of the study, will be provided with **CCI** [REDACTED]

(Sections 6.1.2 and 8.4.6).

Vital sign measurements in a supine position should be preceded by at least 5 minutes of rest for the participant in a quiet setting without distractions (eg, television, cell phones) and will consist of one pulse, one body temperature, and 3 blood pressure measurements

(3 consecutive blood pressure readings will be recorded at intervals of at least 1 minute). The average of the 3 blood pressure readings will be recorded on the eCRF. In addition, CCI

CCI should be CCI in the CCI.

These assessments should preferably be done in the morning. If CCI is confirmed during the test, it should be reported as an AESI including symptoms related to the measurement of CCI if present (Section 8.4.6).

For information on how AEs based on vital sign results should be recorded and reported, see Section 8.4.4.

Body weight will be measured at the study centre at study visits. There will be safety monitoring of body weight from the home-based monitoring devices, or as an alternative, paper diaries can be used for capturing the information. A body weight change of CCI kg per CCI is regarded as a CCI weight change and needs to be followed up by the investigator.

The investigator will have direct access to the online data for their participants using digital devices. If there is a significant weight gain, the investigator will contact the participant immediately and arrange a clinic visit to assess health status. Participants with paper diaries will be instructed to contact the study staff if there is a significant weight gain.

Participants will also be advised to self-monitor and contact the investigator with any concerns.

8.3.3 **Electrocardiograms**

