4.2.5.1 Definition

Estimand is defined in section 4.2. Supine blood pressure will be analysed.

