4.6.6 Vital Signs

4.6.6.1 Definitions and Derivations

Following Vital signs will be presented:

- Body Temperature (C)
- Body Weight (kg)
- Pulse (beats/min)
- Standing Diastolic Blood Pressure (mmHg)
- Supine Diastolic Blood Pressure (mmHg)
- Standing Systolic Blood Pressure (mmHg)
- Supine Systolic Blood Pressure (mmHg)

Treatment emergent

A treatment emergent abnormality is defined as either of below:

- A switch in parameter from normal at baseline to abnormal at post-baseline accordingly to predefined criteria, see below for predefined criteria.
- A baseline value that met the criteria for abnormality and the post-baseline value is more extreme (further from the limit), see below for predefined criteria.

Predefined criteria used for shift tables and treatment emergent reporting

The following definitions of vital sign abnormalities will be used for specified parameters:

- Body weight (kg): Low < 50, Normal \geq 50 and \leq 130, High > 130
- Body temperature (C): Low < 35, Normal \geq 35 and \leq 37.5, High > 37.5
- Supine Systolic blood pressure (mmHg): Low < 95, Normal \geq 95 and \leq 140, High > 140

- Supine Diastolic blood pressure (mmHg): Low < 60, Normal \geq 60 and \leq 100, High > 100

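### The SAP gives blood pressure abnormality limits for supine readings only, so a low standing reading can miss every measurement-based count and reach a categorical table only as a reported AE

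*Protocol*

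**What the plan says.** **Collection.** The Schedule of Activities (Protocol 1.3) has a row for "Vital signs (supine and standing blood pressure and pulse"), marked at every visit from 1 to 7, with repeats at 60, 120 and 180 minutes at Visit 2. Protocol 8.3.2 agrees: "Vital signs will include supine and standing blood pressure, pulse, and body temperature measurements".

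**Reporting commitment.** Protocol 9.4.3.2 states "Vital sign parameters (supine and standing blood pressure, pulse, and body temperature) will be presented for each treatment group". The same section says that "predefined criteria for treatment-emergent changes in relevant vital sign parameters (eg, systolic and diastolic blood pressure) will be provided in the SAP". It does not say which posture those criteria must cover.

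**SAP limits.** SAP 4.6.6.1 includes "Standing Systolic Blood Pressure (mmHg") and its diastolic counterpart in the list of vital signs to be presented. It then sets low, normal and high ranges for body weight, body temperature, supine systolic and supine diastolic pressure. The systolic entry begins "Supine Systolic blood pressure (mmHg): Low < 95", and the supine diastolic Low limit is below 60 mmHg. Standing pressure and pulse have no limits.

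**SAP outputs.** SAP 4.6.6.2 plans by-visit descriptive statistics for all vital signs, listings, a treatment-emergent table, and a shift table from baseline to maximum. For key objectives 9 and 10, SAP 4.2.5.1 states "Supine blood pressure will be analysed".

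**The concern.** This is a safety study, and hypotension is one of its named risks. Table 2 of the protocol (Section 2.3.3) attributes it to vasodilation with zibotentan and adds that dapagliflozin's osmotic diuresis may lower pressure further. The benefit/risk conclusion (Section 2.3.5) names it again. Standing pressure is collected throughout, yet the table that counts participants who become low uses supine readings alone.

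What is at stake is a count. With about 22 participants per arm, one or two people with low standing pressure can be lost in a by-visit mean. Listings contain the values but do not summarise them by arm.

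**Working it through.** The plan states no figure on this point, so the check traces where a low standing reading could be counted.

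**1. Each output in turn**

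| Output | Source | Counts a low standing reading? |
|---|---|---|
| By-visit values and change from baseline | SAP 4.6.6.2 | Included, but not as a count |
| Listings | SAP 4.6.6.2 | Included, but not as a count |
| Treatment-emergent vital signs | SAP 4.6.6.1, 4.6.6.2 | No: depends on predefined limits, and standing pressure has none |
| Shift table | SAP 4.6.6.2 | No: same limits, and runs to the maximum |
| Objective measurement | SAP 4.6.8.1, 4.6.8.2 | Only if the redacted criterion is met |
| AE tables by SOC and PT; AESI tables | SAP 4.6.2.2, 4.6.8.2 | Only if reported as an AE (and, for AESI, on the PT list) |
| Key objectives 9 and 10 | SAP 4.2.5 | No: supine pressure, analysed as a continuous variable |

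Because the shift table runs to the maximum, the treatment-emergent table is the only limit-based output aimed at low pressure in either posture.

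**2. How far the AE route reaches**

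Under Protocol 8.4.4, a deterioration in a mandated vital sign is reported as an AE only if it is serious, is the reason for stopping the IMP, or is clinically relevant in the investigator's judgement. Accompanying signs or symptoms are themselves reported as the AE. Table 2 says that the roughly 5 mmHg reductions seen with zibotentan have usually been asymptomatic. The AE route is therefore weakest for the pattern the protocol itself describes.

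**3. The uncounted range**

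The event name and figures of the objective measurement are redacted. The visible wording suggests a change of stated size within a stated time. As an assumption, let it be met by a systolic fall of at least d mmHg. With supine systolic S and standing systolic T in whole mmHg, a reading escapes both measurement-based tables on the systolic side when

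S ≥ 95, T ≤ 94 and S − T ≤ d − 1.

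The highest such S is 94 + (d − 1). The lowest such T is 95 − (d − 1).

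| d (assumed) | Supine range | Lowest standing value |
|---|---|---|
| 10 | 95 to 94 + 9 = 103 | 95 − 9 = 86 |
| 20 | 95 to 94 + 19 = 113 | 95 − 19 = 76 |
| 30 | 95 to 94 + 29 = 123 | 95 − 29 = 66 |

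At d = 2 the range is the single pair S = 95, T = 94, so some gap exists for any d of 2 mmHg or more. The same reasoning applies to diastolic pressure around 60 mmHg. A reading must also miss any second limb of the redacted criterion, so the table shows what is possible and not how often it occurs.

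**4. An illustration**

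A participant reads 98/62 supine and 88/58 standing. Both supine values are Normal under SAP 4.6.6.1. Both standing values lie below the figures that would be Low if supine. The falls are 98 − 88 = 10 systolic and 62 − 58 = 4 diastolic. Unless falls of that size meet the redacted criterion, this reading is counted only if someone reports it as an AE.

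**The case against.** The strongest reply is that standing pressure is not ignored. It is summarised by visit and arm, so a mean difference would show, and individual values are listed. Hypotension judged clinically relevant, or its symptoms, would enter the AE tables whatever the posture. All of that stands. A reader might infer that low standing pressure appears in no categorical safety table at all; the AE tables by SOC and PT, and possibly the AESI tables, rule that out.

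A reader might also infer that the SAP breaks a protocol commitment. It does not. Protocol 9.4.3.2 promises that standing pressure will be presented, and the by-visit summaries do that. Its promise of abnormality criteria names no posture. Pulse has no limits either, so not every listed parameter was meant to have them.

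Supine pressure is the standardised measurement (Protocol 8.3.2: at least five minutes of rest and the average of three readings). Using it for limits and for key objectives 9 and 10 is a defensible choice. That supports supine as the main analysis. It does not explain why standing readings have no count when they are collected and listed as parameters.

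Finally, the AESI categories are largely redacted, so one of them may capture low pressure. That cannot be excluded. But SAP 4.6.8.1 classifies those categories from PT lists, so they depend on AE reporting. The one measurement-based exception is the objective measurement already considered.

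**Conclusion.** The gap is real but narrow. A low standing reading that misses the objective-measurement criterion and is not reported as an AE is counted in no categorical table; it contributes only to descriptive statistics and listings.

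No frequency can be attached to this. The documents give no mean, spread or usual postural change for blood pressure in this population, and the one relevant criterion is redacted. The uncounted range in mmHg follows from the SAP's own limit once a fall criterion is assumed.

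It would also go too far to say that the comparison between arms is biased. The missing limits apply equally to placebo, and nothing in the documents shows a differential effect. The supportable conclusion is that the SAP's counts are less sensitive to a named risk than the collected data allow. It is worth correcting because the correction is cheap.

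**What to change.** In SAP 4.6.6.1, extend the existing Low limits to standing systolic pressure (below 95 mmHg) and standing diastolic pressure (below 60 mmHg), and state that they serve tabulation only and carry no consequence for participant management. These are the figures in exclusion criterion 22 (Protocol 5.2), which defines hypotension without specifying posture. In SAP 4.6.6.2, present treatment-emergent Low for supine, for standing, and for either position. If the sponsor prefers to keep supine limits only, the SAP should say so and give the reason.

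The cost is SAP wording and a few table rows, with no new data or visits. The downside is that limits written for supine readings will flag somewhat more standing readings, in all arms including placebo; the by-position display and the placebo column let a reader judge that. Repeating the MMRM on standing pressure for key objectives 9 and 10 is optional.

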9.4.3.3 Laboratory Assessments

Laboratory parameters will be presented for each treatment group.

For each scheduled post-baseline visit, descriptive statistics for all clinical chemistry, electrolyte, coagulation, and haematology parameters will be presented for observed values and change from baseline.

Elevation in liver parameters for assessment of Hy's law (see Appendix E) will be done and reported appropriately if potential cases have been identified during the course of the study.

Key participant information will be presented for participants with treatment-emergent changes in laboratory parameters outside of predefined criteria.

Supportive laboratory listings will cover observed values and changes from baseline for each individual participant as well as abnormalities.

Details of laboratory analyses including definition of abnormality criteria (eg, definition of low, normal, high) and study-specific predefined criteria for treatment-emergent changes in relevant laboratory parameters will be provided in the SAP.

9.4.3.4 Electrocardiograms

Electrocardiogram findings will be listed for each participant and will include the ECG parameters (where applicable) and changes from baseline, assessment by the investigator (normal/abnormal not clinically significant/abnormal clinically significant) and details of any

abnormalities. ECG parameters will be summarised by time-point including changes from baseline. The baseline for the safety ECG parameters will be the results obtained pre-dose on Day 1.

ECG parameters to be tabulated will be provided in the SAP.

9.4.4 Exploratory endpoints

9.4.4.1 Exploratory Pharmacokinetic Endpoints

Plasma concentrations of zibotentan and dapagliflozin will be summarised by treatment group, visit, and time-point based on the PKS.

Additional PK analyses may be conducted as appropriate but will be reported outside the CSR.

Further details of this will be provided in the SAP.

9.4.4.2 Exploratory Pharmacodynamic and Biomarker Endpoints

The exploratory PD and biomarker endpoints described in Section 8.2.2.3 will be summarised by treatment group and time-point based on the FAS.

Further details on this will be provided in the SAP.

9.4.4.3 Exploratory PRO Endpoints

Results for patient-reported outcomes will be summarized by treatment group for FAS.

Further details on this will be provided in the SAP.

9.4.4.4 Other Exploratory Endpoints

Percentage and absolute change in [CC1] and/or [CC1] assessed using [CC1] at Week 6, change in eGFR at Week 1, Week 6, and evaluation of changes in blood biomarkers across time course of the study will be analysed according to treatment group. For details on exploratory objectives and endpoints, see Section 3.

Further details about analyses of exploratory endpoints will be provided in the SAP.

9.4.4.5 Exploratory Research and Optional Genetic Research

The following analyses will not be part of the CSR:

- Evaluation of changes in other blood and urine biomarkers, not outlined in this protocol, but relevant to liver diseases and drug-related mechanisms over the time course of the study.

- Optional exploratory research into genes/genetic variation that may influence response to treatment.

Analyses for these exploratory objectives will be described in a separate analysis plan and results will be presented separately from the main CSR.

9.5 Interim Analyses

Not applicable.

9.6 Data Monitoring Committee

A DMC will monitor ongoing safety/tolerability data (including monitoring of modified CCI [REDACTED] and CCI [REDACTED] including CCI [REDACTED]) and have the authority to unblind a participant's intervention assignment due to safety concerns if warranted. The DMC will be asked to meet at regular intervals and may also meet more often if they think it is needed from a safety perspective. The DMC may recommend stopping further recruitment and/or treatment of participants in a treatment group at any time after a comprehensive assessment of safety data. The recommendation will be evaluated by an unblinded senior manager who will provide a decision based on the DMC recommendation to the study team. Further details will be provided in a separate DMC charter.

For details on the DMC, refer to Appendix [A 5](#).

10 SUPPORTING DOCUMENTATION AND OPERATIONAL CONSIDERATIONS

Appendix A Regulatory, Ethical, and Study Oversight Considerations

A 1 Regulatory and Ethical Considerations

- This study will be conducted in accordance with the protocol and with the following:
 - Consensus ethical principles derived from international guidelines including the Declaration of Helsinki and Council for International Organizations of Medical Sciences (CIOMS) International Ethical Guidelines
 - Applicable ICH GCP Guidelines
 - Applicable laws and regulations
- The protocol, protocol amendments, ICF, Investigator's Brochure, and other relevant documents (eg, advertisements) must be submitted to an IRB/IEC by the investigator and reviewed and approved by the IRB/IEC before the study is initiated.
- Any revised protocol will require IRB/IEC and applicable Regulatory Authority approval before implementation of changes made to the study design, except for changes necessary to eliminate an immediate hazard to study participants.
- AstraZeneca will be responsible for obtaining the required authorisations to conduct the study from the concerned Regulatory Authority. This responsibility may be delegated to a CRO, but the accountability remains with AstraZeneca.
- The investigator will be responsible for providing oversight of the conduct of the study at the site and adherence to requirements of 21 CFR 312.120, ICH guidelines, the IRB/IEC, European Regulation 536/2014 for clinical studies (if applicable), European Medical Device Regulation 2017/745 for clinical device research (if applicable), and all other applicable local regulations.

Regulatory Reporting Requirements for SAEs

- Prompt notification by the investigator to AstraZeneca of an SAE is essential so that legal obligations and ethical responsibilities towards the safety of participants and the safety of a study intervention under clinical investigation are met.
- AstraZeneca has a legal responsibility to notify both the local regulatory authority and other regulatory agencies about the safety of a study intervention under clinical investigation. AstraZeneca will comply with country-specific regulatory requirements relating to safety reporting to the regulatory authority, IRB/IEC, and investigators.
- In the EU, the Sponsor will comply with safety reporting requirements and procedures as described in the European Clinical Trials Regulation (EU) No 536/2014. All SUSARs to investigational medicinal product will be reported to the EudraVigilance database within the required regulatory timelines.

- For all studies except those utilising medical devices, investigator safety reports must be prepared for SUSARs, according to local regulatory requirements and sponsor policy and forwarded to investigators as necessary.
 - European Medical Device Regulation 2017/745 for clinical device research (if applicable), and all other applicable local regulations
- An investigator who receives an investigator safety report describing an SAE or other specific safety information (eg, summary or listing of SAEs) from AstraZeneca will review and then file it along with the Investigator's Brochure and will notify the IRB/IEC, if appropriate according to local requirements.

Regulatory Reporting Requirements for Serious Breaches of Protocol or GCP

Prompt notification by the Investigator to AstraZeneca of any (potential) serious breach of the protocol or regulations is essential so that legal and ethical obligations are met.

A “serious breach” means a breach likely to affect to a significant degree the safety and rights of a participant or the reliability and robustness of the data generated in the clinical study.

AstraZeneca will comply with country-specific regulatory requirements relating to serious breach reporting to the regulatory authority, IRB/IEC, and investigators.

Where the EU Clinical Trials Regulation 536/2014 applies, AstraZeneca has in place processes to enter details of serious breaches into the European Medicines Agency CTIS. It is important to note that redacted versions of serious breach reports will be available to the public via CTIS.

If any (potential) serious breach occurs in the course of the study, Investigators or other site personnel will inform the appropriate AstraZeneca representatives immediately.

In certain regions/countries, AstraZeneca has a legal responsibility to notify both the local regulatory authority and other regulatory agencies about such breaches.

The investigator should have a process in place to ensure that:

- The site staff or service providers delegated by the investigator/institution are able to identify the occurrence of a (potential) serious breach
- A (potential) serious breach is promptly reported to AstraZeneca or delegated party, through the contacts (email address or telephone number) provided by AstraZeneca.

A 2 Financial Disclosure

Investigators and sub-investigators will provide AstraZeneca with sufficient, accurate financial information as requested to allow AstraZeneca to submit complete and accurate financial certification or disclosure statements to the appropriate regulatory authorities. Investigators are responsible for providing information on financial interests during the study and for one year after completion of the study.

A 3 Informed Consent Process

- The investigator or their representative will explain the nature of the study to the participant and answer all questions regarding the study.
- Participants must be informed that their participation is voluntary, and they are free to refuse to participate and may withdraw their consent at any time and for any reason during the study. Participants will be required to sign a statement of informed consent that meets the requirements of 21 CFR 50, local regulations, ICH guidelines, privacy and data protection requirements, where applicable, and the IRB/IEC or study centre.
- The medical record must include a statement that written informed consent was obtained before the participant was enrolled in the study and the date the written consent was obtained. The authorised person obtaining the informed consent must also sign the ICF.
- If new information requires changes to the ICF, consider if participants must be re-consented and if so, this must be to the most current version of the ICF(s) during their participation in the study.
- A copy of the ICF(s) must be provided to the participant.

Participants who are rescreened are required to sign a new ICF.

The ICF will contain a separate section that addresses and documents the collection and use of any mandatory and/or optional Human Biological Samples. The investigator or authorised designee will explain to each participant the objectives of the analysis to be done on the samples and any potential future use. Participants will be told that they are free to refuse to participate in any optional samples or future use, and may withdraw their consent at any time and for any reason during the retention period.

A 4 Data Protection

- Participants will be assigned a unique identifier by AstraZeneca. Any participant records or datasets that are transferred to AstraZeneca will contain the identifier only; participant names or any information which would make the participant identifiable will not be transferred.

- The participant must be informed that their personal study-related data will be used by AstraZeneca in accordance with local data protection law. The level of disclosure and use of their data must also be explained to the participant in the informed consent.
- The participant must be informed that their medical records may be examined by Clinical Quality Assurance auditors or other authorised personnel appointed by AstraZeneca, by appropriate IRB/IEC members, and by inspectors from regulatory authorities.
- The participant must be informed that data will be collected only for the business needs. We will only collect and use the minimum amount of personal data to support our business activities and will not make personal data available to anyone (including internal staff) who is not authorised or does not have a business need to know the information.
- The participant must be informed that in some cases their data may be pseudonymised. The General data Protection Regulation (GDPR) defines pseudonymisation as the processing of personal data in such a way that the personal data can no longer be attributed to a specific individual without the use of additional information, provided that such additional information is kept separately and protected by technical and organisational measures to ensure that the personal data are not attributed to an identified or identifiable natural person.

Personal Data Breaches

A 'personal data breach' means a breach of security leading to the accidental or unlawful destruction, loss, alteration, unauthorised disclosure of, or access to, personal data transmitted, stored or otherwise processed.

- In compliance with applicable laws, the Data Controller for the processing activity where the personal data breach occurred (AstraZeneca or respectively the site), will notify the data protection authorities without undue delay within the legal terms provided for such notification and within the prescribed form and content.
- Whilst AstraZeneca has processes in place to deal with personal data breaches it is important that investigators that work with AstraZeneca have controls in place to protect patient data privacy.

The investigator should have a process in place to ensure that:

- They allow site staff or service providers delegated by the investigator/institution to identify the occurrence of a (potential) personal data breaches.
- Any (potential) personal data breach is promptly reported to AstraZeneca or delegated party, through the contacts (e-mail address or telephone number) provided by AstraZeneca.

AstraZeneca and the site must demonstrate that they:

- Have taken all necessary steps to avoid personal data breaches and
- Have undertaken measures to prevent such breaches from occurring in the first place and to mitigate the impact of occurred data breaches (eg, applying encryption, maintaining and keeping systems and IT security measures up-to-date, regular reviews and testing, regular training of employees, and developed security policies and standards).
- Where possible, have developed an internal data breach reporting and investigation process and internal protocols with guidance on how to respond swiftly and diligently to the occurrence of a personal data breach.
- Where it has not been possible to develop an internal data breach reporting and investigation process, the site follows AstraZeneca's instructions.

Notification of personal Data Breach to participants:

- Notification to participants is done by the site for the data breaches that occurred within the processing activities for which the site is the Data Controller and for data breaches occurred within the processing activities of AstraZeneca as the Data Controller, the notification is done in collaboration with the site and is performed by the site and/or Principal Investigator, acting on behalf of AstraZeneca, so that AstraZeneca has no access to the identifying personal information of the participants. The site and/or Principal Investigator shall conduct the notification by contacting the participants using the information that they gave for communication purposes in clinical research.
- If a personal data breach occurs in a processor's systems, engaged by AstraZeneca, the processor under contractual obligations with AstraZeneca promptly and in due course after discovering the breach notifies AstraZeneca and provides full cooperation with the investigation. In these cases, to the extent AstraZeneca is the Data Controller for the processing activity where the breach occurred, it will be responsible for the notification to data protection authorities and, if applicable, to participants. If the personal data breach needs to be notified to the participants, the notification to participants is done in collaboration with the site and is performed by the site and/or Principal Investigator, acting on behalf of the Sponsor, so that AstraZeneca has no access to the identifying personal information of the participants.
- If a personal data breach involving an AstraZeneca's representative device (ie, Study Monitor laptop), AstraZeneca representative will provide AstraZeneca with all of the information needed for notification of the breach, without disclosing data that allows AstraZeneca directly or indirectly to identify the participants. The notification will be done by AstraZeneca solely with the information provided by the Study Monitor and in no event with access to information that could entail a risk of re-identification of the participants. If the data breach must be notified to the data subjects, the notification will

be done directly by the Study Monitor in collaboration with the site and/or Principal Investigator, acting on behalf of the Sponsor, so that AstraZeneca has no access to the identifying personal information of the participants. The contract between AstraZeneca and the Study Monitor shall expressly specify these conditions.

- The contract between the site and AstraZeneca for performing the clinical research includes the provisions and rules regarding who is responsible for coordinating and directing the actions in relation to the breaches and performing the mandatory notifications to authorities and participants, where applicable.

A 5 Committees Structure

A DMC will be set up for this study in accordance with the AstraZeneca charter for data review committees.

The safety of all AstraZeneca clinical studies is closely monitored on an ongoing basis by AstraZeneca representatives in consultation with Patient Safety. Issues identified will be addressed; for instance, this could involve amendments to the protocol and letters to investigators.

A 6 Dissemination of Clinical Study Data

Any results both technical and lay summaries for this trial, will be submitted to EU CTIS within a year from global End of Trial Date in all participating countries, due to scientific reasons, as otherwise statistical analysis is not relevant.

A description of this clinical study will be available on www.astrazenecaclinicaltrials.com [<http://www.clinicaltrials.gov>] and <https://euclinicaltrials.eu/> as will the summary of the main study results when they are available. The clinical study and/or summary of main study results may also be available on other websites according to the regulations of the countries in which the main study is conducted. Describe sponsor -specific policy on provision of study results.

A 7 Data Quality Assurance

- All participant data relating to the study will be recorded on eCRF unless transmitted to AstraZeneca or designee electronically (eg, laboratory data). The investigator is responsible for verifying that data entries are accurate and correct by electronically signing the eCRF.
- The investigator must maintain accurate documentation (source data) that supports the information entered in the eCRF.
- The investigator must permit study-related monitoring, audits, IRB/IEC review, and regulatory agency inspections and provide direct access to source data documents.
- Monitoring details describing strategy, including definition of study-critical data items and processes (eg, risk-based initiatives in operations and quality such as Risk

Management and Mitigation Strategies and Analytical Risk-based Monitoring), methods, responsibilities and requirements, including handling of non-compliance issues and monitoring techniques (central, remote, or on-site monitoring) are included in the Monitoring Plan

- AstraZeneca or designee is responsible for medical oversight throughout the conduct of the study which includes clinical reviews of study data in accordance with the currently approved protocol. Monitoring details describing clinical reviews of study data from a medical perspective are included in more detail in the Medical Oversight Plan.
